13.2 Sample Size, Accrual Rate and Study Duration

The study is designed with 80% power and confidence level of 95% to detect an absolute 20% difference between diagnostic procedure arms in diagnostic yield with two-sided hypothesis testing. The Type I error probability associated with this test of this null hypothesis is 0.05. We will use an uncorrected chi-squared statistic to evaluate this null hypothesis.

Total patient cohort will be 136; sixty-eight in each arm with a ratio of control to experimental subjects of 1:1. We expect to enroll the patients in a 2-year span as our center has a volume of approximately 3 patients per week

13.3 Stratification Factors

Stratification factors for the study will be:

- Nodule size (< 20 mm vs \geq 20 mm)
- Distance to the pleura (< 10 mm vs \geq 10 mm)
- Presence of bronchus sign (Binomial: Yes vs No)

13.4 Interim Monitoring Plan

Data reporting and monitoring plan can be found in Section 12.

13.5 Analysis of Primary Endpoints

The overall diagnostic yield will be calculated by adding the number of true positives (TP) for both malignancy and benign disease in the numerator and dividing by the total number of procedures performed for each arm of the study.

Proportions will be compared with the Chi-Square Test as this test is equivalent to the z-test of two proportions (26). A p-value <0.05 will be considered as statistically significant.

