1. OBJECTIVES

In this study, we hypothesize that CBCT-guided NB would improve diagnostic yield for peripheral lung nodules as compared to NB alone. We aim to find the difference in the diagnostic yield between both groups (Percentage of lesions tested positive).

μ_0 = Diagnostic yield NB-alone = Diagnostic yield CBCT-guided NB μ_1 = Diagnostic yield CBCT-guided NB > Diagnostic yield NB-alone
 μ_0 = Null Hypothesis
 μ_1 = Alternate Hypothesis

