For patients that continue in the study due to a benign or non-diagnostic biopsy, information related to any additional procedural complications (i.e. pneumothorax or pneumonia) will be collected.

Post-procedure (up to 180 days) Assessment

For patients that continue in the study due to a benign or non-diagnostic biopsy. Pathology and disease information will be obtained from any additional diagnostic assessments, interventions or treatments associated with the study related nodule(s).

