13 STATISTICAL CONSIDERATIONS

Previous studies have shown variable CBCT diagnostic yields, but prospective evidence remains poor. Sobieszczyk et al. published retrospective case series of 22 patients with combination of ENB, R-EBUS, CBCT and TBAT reporting a diagnostic yield of 77.2%. However, authors have not clarified how such yield was calculated. Ali et al. reported prospective case series of 40 patients with combination of ultrathin bronchoscope, ENB and CBCT achieving diagnostic yield of 90% (11). However, the likely explanation for such high yield is inclusion of nodules with bronchus sign only, and inclusion of non-specific inflammation in diagnostic yield calculation. Casal et al. combined thin/ultrathin bronchoscope, R-EBUS and CBCT in a prospective series of 20 patients (19). The median size of the nodules in the series was 21 mm, and diagnostic yield was 70%. In their series non-specific inflammation were considered diagnostic if confirmed by surgical pathology or resolved or improved during follow-up period. Hofenforst-Schmidt et al. published one of the earliest series on CBCT and peripheral pulmonary nodules (25). It was a prospective series of 33 patients divided into subgroups bases on nodule size \leq 20 mm, and $>$ 20 mm. The reported diagnostic yield was 75% in subgroup of nodules \leq 20 mm (mean size 15 mm) and was 67% in subgroup of nodules $>$ 20 mm (mean size 30mm). In 2018, Pritchett et al. published one of the larger retrospective series of 74 patients with 92 nodules combining ENB and CBCT-AF (20). The median lesion size was 16 mm in their series and diagnostic yield of 83.7%.

The overall diagnostic yield of currently available ENB alone is 67% based on meta-analysis of 11 studies (17). We aim to detect an absolute 20% difference between CBCT+NB and NB alone

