13.1 Study Design/Endpoints

Primary outcome of diagnostic yield will be determined from the results of NB as compared with CBCT-guided NB. A biopsy that results in a specific diagnosis, either malignant or benign (i.e. granuloma, inflammation, fibrosis, infection) will be assumed to be a true positive with appropriate follow up as indicated for up to 6 months. Atypia or lung parenchyma without pathologic findings on final pathology reads will be considered non-diagnostic. If a nondiagnostic lesion resolved, stayed stable or decreased in size on follow-up CT for at least 6 months after the index procedure then this will be presumed benign and classified as a true negative for the purposes of calculating sensitivity and prevalence of malignancy, as well as for diagnostic accuracy.

Confirmation of the diagnosis by surgery, CT guided TTNA or repeat imaging will be recorded for those patients who have nondiagnostic results from the study procedures. If the subject is referred for surgery, the surgical pathology will be considered the final diagnosis.

If the subject has follow-up imaging that shows a decrease in size or resolution of the nodule, the nodule will be determined to be of benign etiology if the study pathology yields a benign diagnosis (granuloma, inflammation, fibrosis, infection).

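### The primary endpoint has no single unit of analysis: yield is defined per lesion, calculated per procedure and sized per patient, with no index nodule tied to it

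*Combined protocol and SAP*

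**What the plan says.** The combined protocol and SAP expresses the endpoint, or a part of it, in several units:

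- **Lesions.** Section 1 (Objectives) glosses diagnostic yield as "Percentage of lesions tested positive".
- **Biopsies.** Section 13.1 attaches a true positive to "A biopsy that results in a specific diagnosis, either malignant or benign".
- **Procedures.** Section 13.5 calculates yield by putting true positives, malignant and benign alike, "in the numerator and dividing by the total number of procedures performed for each arm of the study".
- **Patients.** Section 13.2 sets the sample size at 136 patients, 68 per arm, and names an uncorrected chi-square test. Section 13.6 reports its secondary yields per participant.

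The 180-day assessment in Section 3.6 collects results from later work-up "associated with the study related nodule(s", with the plural left open. Sections 3.3 and 3.4 do not limit a patient to one nodule. Section 3.6 also refers to a planned target location and Section 5.7 to a target nodule, both in the singular, but neither is linked to the endpoint. The three factors in Section 13.3 (size, distance to the pleura, bronchus sign) all describe a nodule. Section 13.6 names generalized estimating equations (GEE) for the secondary analysis of factors affecting yield, without stating the cluster. Section 13.7.2, headed as the evaluation of the primary efficacy endpoint, is marked not applicable.

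**The concern.** If every patient has one nodule sampled in one procedure, the units coincide and nothing is lost. The plan does not say that this will be so, and it gives no counting rule for a patient in whom two nodules are sampled. Two different things can then go wrong, depending on how the text is applied:

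- **Lesion-level positives over procedures.** The numerator can grow faster than the denominator, and yield is overstated.
- **Lesions in both numerator and denominator.** The chi-square test treats two nodules from one patient as independent, so its standard error is too small if their results are positively correlated.

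The Section 13.3 factors are also undefined for a patient whose two nodules fall in different categories, for example 12 mm and 25 mm.

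The trial is nonblinded (Section 1.1). With two stated definitions of the primary endpoint, more than one primary result could be calculated from the same data.

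**Working it through.** **1. The plan's own sample size.** Inputs: control yield 67% and a 20-point difference (Section 13), hence 87% in the CBCT arm; two-sided 5% level, 80% power and uncorrected chi-square (Section 13.2).

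n per arm = [1.96 × √(2 × 0.77 × 0.23) + 0.8416 × √(0.67 × 0.33 + 0.87 × 0.13)]² / 0.20² = (1.166 + 0.487)² / 0.04 ≈ 68.3, rounded up to 69. With 68 per arm, power is 79.8%. The stated 68 is therefore reproduced to within one patient, taking one result per patient.

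**2. Lesion-level positives over procedures.** Calculated yield = per-lesion yield × lesions per procedure.

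- It passes 100% in the CBCT arm once lesions per procedure exceed 1/0.87 = 1.149.
- The documents give no expected number of nodules per patient for this trial. For illustration, Section 13 cites a "retrospective series of 74 patients with 92 nodules combining ENB and CBCT-AF", which is 92/74 = 1.243 per patient.
- At 1.243 the formula gives 0.87 × 1.243 = 108.2% and 0.67 × 1.243 = 83.3%. The 20-point difference becomes 24.9 points.
- At an assumed 1.10 it gives 95.7% and 73.7%.
- Applied to the cited series itself, 0.837 × 92 = 77 positives, and 77/74 = 104%. This assumes that the 83.7% is per nodule; Section 13 does not state its denominator.

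**3. Lesions in both places.** Assume at most two nodules per patient, so 92 nodules in 74 patients means 18 patients with two and 56 with one. Then Σm = 56 + 36 = 92 and Σm² = 56 + 72 = 128.

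Variance inflation = 1 + (128/92 − 1) × ICC = 1 + 0.391 × ICC.

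True size = 2 × P(Z > 1.96/√inflation).

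| Assumed ICC | Variance inflation | True size of nominal 5% test |
|---|---|---|
| 0.1 | 1.039 | 5.5% |
| 0.3 | 1.117 | 6.4% |
| 0.5 | 1.196 | 7.3% |
| 0.7 | 1.274 | 8.2% |

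Steps 2 and 3 are alternatives. They do not add up.

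**The case against.** The strongest reply is that Section 13.5 has an ordinary reading: one patient, one procedure, diagnostic or not. It calls the results proportions, it never says that the numerator counts lesions, and it agrees with the patient-based Section 13.2. On that reading yield cannot exceed 100% and the observations are independent. Only the parenthesis in Section 1 says lesions, and several passages speak of the target in the singular. This may well be what the authors intend. But the Section 1 definition and the open plural in Section 3.6 remain, and even on the ordinary reading nothing says what makes a procedure diagnostic when two nodules are sampled and one is positive.

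It is also fair to object that Section 13.3 does not say whether its factors apply at randomisation or in the analysis, and that Section 1.1 describes only block randomisation. The gap matters either way, since both uses need one value per patient.

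Four stronger inferences are tempting but not supported:

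- **That this trial will report yields above 100%.** That needs the Section 1 lesion count in the numerator, the Section 13.5 denominator, and enough patients with several sampled nodules.
- **That the operator may pick the favourable nodule afterwards.** Section 13.1 rests the result on the biopsy and the final pathology read. The plan lacks a counting rule; it does not grant a choice.
- **That no target is ever identified.** Sections 3.6 and 5.7 refer to one. It is simply not tied to the endpoint or the factors.
- **That the sample size is wrong.** It reproduces.

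**Conclusion.** The inconsistency is in the current text and affects the definition of the sole primary endpoint, so it should be corrected before analysis. Its practical size depends on how many patients have more than one nodule sampled, which the documents do not give. On the illustrative mix, the type I error of a per-lesion test is about 5.5% to 8.2% for ICC 0.1 to 0.7. This is modest at low correlation and approaches the nominal 5% if few patients have several nodules. Those figures rest on one cited retrospective series, a maximum of two nodules per patient and assumed correlations, so they are hypothetical and not forecasts for this trial. With one result per patient neither problem arises.

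**What to change.** - Name one index nodule per patient before randomisation and record it in one CRF field. Use the same nodule for the Section 13.3 factors and for the primary endpoint.
- In Section 13.5, define yield as patients whose index nodule receives a qualifying diagnosis, divided by patients in the arm, with one result per patient. Align Section 13.1, and replace the lesion wording in Section 1 to match.
- Report other sampled nodules in a secondary per-nodule analysis, using the GEE approach already named in Section 13.6 with the patient stated as the cluster.
- State separately whether the denominator is patients randomised or patients who undergo the procedure. That is a question of analysis population, and the unit correction does not depend on it.

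The cost is wording in Sections 1, 13.1, 13.3, 13.5 and 13.6 plus the CRF field. The small downside is that results from extra nodules leave the primary analysis. The planned 68 per arm does not change.

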1.1 Study Design

- We propose a prospective, randomized, two- arm, single-center nonblinded, controlled clinical trial to evaluate the diagnostic yield of lung biopsy in NB-alone and CBCT-guided NB.
- Randomization schedule will be determined in advance by computer with the intent of a 1:1 randomization scheme.
- For randomization, Block randomization will be used. The block randomization method is designed to randomize subjects into groups that result in equal sample sizes. This method is used to ensure a balance in sample size across groups over time. This was decided based on the limited access to the Cone Beam room, which is available exclusively once a month (the first Friday of each month).
- All bronchoscopies will be performed under general anesthesia and ROSE will be available upon physician request/preference.
- Radial probe-EBUS and fluoroscopy will be utilized in all cases.
- Tissue samples will be obtained using multimodality tools, including cytology brush, fine needle for aspiration, biopsy forceps, and bronchoalveolar lavage.
- NB procedure will be performed per product instructions and the institution's standard practice.

CBCT-guided NB procedure arm:

Following intubation, an inspiratory breath-hold maneuver with the adjustable pressure limiting (APL) valve set at 20 cm H₂O will be performed by the anesthesiology provider. This mimic the inspiratory

breath hold done during a CT scan. During the breath-hold maneuver, CBCT will be performed. A dedicated arm attached to the bronchoscopy cart will be utilized to hold the bronchoscope in position so that the operators can leave the room during CBCT scan. Lung nodules will be highlighted using available software (OncoSuite; Philips) during a process known as segmentation. A bronchoscope will be introduced into the airway and then using NB to navigate to the lesion. Nodule segmentation will be visualized in an overlay with live fluoroscopy. Geometric correspondence of augmented fluoroscopy (AF) will be maintained throughout the case while manipulating C-arm angulation, table position, and image-zoom settings. Final catheter position will then be verified in multiple planes with AF. Additional CBCT scans will be acquired when deemed necessary.

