2. BACKGROUND

2.1 Study Disease

Diagnostic sampling of suspicious peripheral lung nodules has become increasingly important, as early diagnosis of malignancy can provide an opportunity for potentially curative resection and improved survival. Traditionally, CT-guided transthoracic needle aspiration (TTNA) was the most accepted modality to obtain tissue diagnosis of suspicious peripheral lung nodules, with a diagnostic yield reported in the literature ranging from 77 to 98% (1–4). However, despite the high diagnostic yield, pneumothorax can occur in up to 35% of patients, with up to 15% requiring chest tube placement, increasing hospital stays and overall healthcare costs (5,6). In contrast, the transbronchial approach the risk of pneumothorax is only around 0.02% to 4.9% (7–10). Furthermore, CT-guided TTNA might be associated with a higher incidence of local recurrence with pleural dissemination when compared with transbronchial or open lung biopsy (11).

Transbronchial biopsy is a safe diagnostic tool recommended for patients with peripheral lung nodules with the limitation of a lower diagnostic yield compared with CT-guided TTNA. The diagnostic yield of transbronchial biopsy guided by fluoroscopy is widely variable, ranging from 18 to 80%, and is strongly dependent on the lesion size (12,13). In order to increase the diagnostic yield of the transbronchial

approach, techniques and devices such as the ultrathin bronchoscope, radial endobronchial ultrasonography with guided sheath (EBUS-GS), electromagnetic navigation bronchoscopy and cone beam CT (CBCT) are becoming widely utilized (11).

ENB allows bronchoscopists to safely navigate to and sample peripheral lung lesions minimally invasively with an acceptable safety profile. Furthermore, the ability to provide concurrent lymph node staging with linear endobronchial ultrasound (EBUS) or assist in nodule localization via pleural dye or fiducial marking in a single procedure could potentially decrease health care costs and improve patient satisfaction (10). However, due to CT to body divergence and atelectasis, increasing diagnostic yield has been an ongoing challenge. Recently, cone beam CT (CBCT) has emerged as a promising adjunct to navigational bronchoscopy, allowing real-time “needle in lesion” static confirmation, with a potential increase in diagnostic yield (14).

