2.4 Rationale

Pulmonary nodules are a common diagnostic problem in daily clinical practice. The results of the National Lung Cancer Screening Trial demonstrated a reduction in lung cancer mortality with screening of patients with low dose CT (15). This has led to an increase in the number of nodules detected requiring appropriate follow up (16). The challenge in the management of pulmonary nodules lies in the necessity to identify the few lung cancers within the vast majority of benign nodules. This created a dilemma for clinicians to decide about further diagnostic modalities to pursue for optimizing yield, minimizing complications while reducing unnecessary benign surgical resections rates. Thus, there is an urgent need for minimally invasive diagnostic techniques with both excellent performance and safety for evaluation of lung nodules. The overall diagnostic yield of currently available electromagnetic navigation bronchoscopy (ENB) technique is 67% based on meta-analysis of 11 studies (17). However, when analyzed more closely, the diagnostic yield appears to be influenced by nodule size and presence of a bronchus sign and it appears to be much lower approaching 47% (7). However, a major limitation of all ENB platforms is the reliance on preoperative CT for planning and navigation as opposed to real-time image guidance. This commonly results in CT body divergence leading to disappointing yields on navigational bronchoscopy. Cone beam computed tomography (CBCT) is a newer modality that emerged as a promising adjunct to navigational bronchoscopy that might mitigate CT to body divergence allowing near real-time confirmatory imaging, with a potential impact on diagnostic yield. However, data on the use of this technology in combination with bronchoscopy is very scant and mostly based on non-randomized studies (18–20).

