13.6 Analysis of Secondary Endpoints

Secondary analysis of the diagnostic yields of BAL cytology, EBUS, NB and EMN-TTNA will be calculated as the proportion of participants with a diagnostic result including on those whom underwent the given procedure. As part of a secondary analysis of procedural and radiographical factors that may impact diagnostic yield, we will examine their effects on diagnostic yields using a logistic regression model which will be estimated using the generalized estimating equations (GEE) approach.

Data regarding procedural complications, radiation exposure, and need of further diagnostic procedures will be prospectively recorded.

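### The primary chi-square test ignores the three stratification factors the protocol names; adjusting for them would gain about 0 to 4 power points, and their role in randomization is not stated

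*Combined protocol and SAP*

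**What the plan says.** Section 13.3 begins "Stratification factors for the study will be" and lists nodule size (cut at 20 mm), distance to the pleura (cut at 10 mm) and bronchus sign (yes or no). It does not say whether they stratify the randomization, the analysis or both.

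Section 1.1 says "For randomization, Block randomization will be used". It justifies this by equal group sizes and limited access to the cone-beam room, and does not mention the factors.

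The planning text in Section 13.2 says "We will use an uncorrected chi-squared statistic to evaluate this null hypothesis". Section 13.5 sets the same test for the primary analysis: "Proportions will be compared with the Chi-Square Test as this test is equivalent to the z-test of two proportions (26". Neither section has strata or covariates.

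Section 13.6 adds a secondary analysis of procedural and radiographic factors: "we will examine their effects on diagnostic yields using a logistic regression model", fitted by GEE. It is not described as an adjusted comparison of the arms.

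On prognosis, Section 2.4 says that "the diagnostic yield appears to be influenced by nodule size and presence of a bronchus sign". Section 13 comments on a series with a 90% yield that "the likely explanation for such high yield is inclusion of nodules with bronchus sign only", along with the counting of non-specific inflammation as diagnostic.

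**The concern.** The protocol treats two of its three factors as reasons why yield differs between studies, then leaves all three out of its own primary comparison. What follows depends on a fact that the plan does not give.

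- **If the factors stratify the randomization and are prognostic,** the arms are balanced on them, but the crude chi-square still counts the between-stratum variation as noise. Its true type I error falls below 5% and power is lost.
- **If they do not stratify the randomization,** the crude test keeps its 5% level, but a chance imbalance in size or bronchus sign stays in the estimate. Any adjusted result produced later would be post hoc.

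All three factors can be known before biopsy, so using them needs no new data and no more patients.

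**Working it through.** **Inputs from the documents.** Two-sided alpha 0.05, 80% power, 68 per arm, uncorrected chi-square (Section 13.2). NB-alone yield 67% and a 20-point absolute difference (Section 13), hence 87% with CBCT.

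**Assumptions, not in the documents.** Equal odds ratios (OR) for size and bronchus sign, the same in both arms; no effect of pleural distance; independent factors, each split 50/50; blocks of 4.

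**1. The plan's own figure.** n per arm = [z₀.₉₇₅√(2p̄(1−p̄)) + z₀.₈₀√(p₀(1−p₀)+p₁(1−p₁))]²/δ². With p̄ = 0.77 the roots are 0.5951 and 0.5781, so n = (1.960×0.5951 + 0.8416×0.5781)²/0.20² = 68.3. Power at 68 is Φ[(0.20√68 − 1.960×0.5951)/0.5781] = Φ(0.835) = 79.8%; exact enumeration gives 80.8%. The stated size is reproduced.

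**2. Why the crude test is conservative under stratified blocks.** Take OR 3 for both factors and a common yield of 67%. The four size-by-sign cells then have yields of 42.7%, 69.1%, 69.1% and 87.0%. Mean within-cell variance is (0.427×0.573 + 2×0.691×0.309 + 0.870×0.130)/4 = 0.196. The crude test uses 0.67×0.33 = 0.221. The ratio is 0.887, so the effective critical value is 1.960/√0.887 = 2.08 and type I error is about 3.7%. Simulation gave 3.8%.

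**3. Power at 67% versus 87%.** Simulation of 40,000 trials per cell (Monte Carlo standard error about 0.1 point for type I error and 0.2 for power). The adjusted test is a main-effects logistic model with standardised risk difference, influence-function variance and a t reference. Its critical value was set so that type I error is 5%.

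| Blocks | OR | Chi-square type I error | Crude power | Adjusted power | Gain (points) |
|---|---|---|---|---|---|
| Stratified | 2 | 4.6% | 81.0% | 81.9% | 0.9 |
| Stratified | 3 | 3.8% | 82.0% | 84.6% | 2.6 |
| Stratified | 4 | 3.1% | 82.5% | 86.1% | 3.6 |
| Unstratified | 2 | 5.1% to 5.3% | 80.9% | 81.2% | 0.3 |
| Unstratified | 3 | 5.1% to 5.3% | 80.9% | 83.1% | 2.2 |
| Unstratified | 4 | 5.1% to 5.3% | 81.3% | 85.1% | 3.8 |

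A second simulation with balanced strata and nominal critical values gave gains at OR 2, 3 and 4 of 0.8, 2.1 and 3.1 points for an 8-stratum Cochran-Mantel-Haenszel (CMH) test, and 1.6, 2.8 and 4.0 for a logistic score test.

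**4. Sensitivity (stratified, then unstratified).**
- No factor matters: adjustment loses 0.2 or 0.7 points. An 8-stratum CMH test under unstratified blocks loses 2.0 (80.4% to 78.4%).
- Size effect vanishes with CBCT, OR 3 otherwise: gain 1.4 or 1.2.
- Bronchus sign in 30% of patients, OR 3: gain 1.8 or 2.1.
- 47% versus 67%, OR 3: 66.3% to 71.0%, or 64.9% to 70.3%.

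**5. Chance imbalance under unstratified blocks.** For two binomials (68, 0.5), a gap of 10 points or more needs at least 7 patients. The exact probability is 26.5% for one factor and 1 − (1 − 0.265)² = 46.0% for at least one of two. At OR 3, yield is 78% with a bronchus sign and 56% without, so each 10-point imbalance moves the crude difference by 0.10×22 = 2.2 points.

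**The case against.** The strongest reply is that nothing here is wrong. Planning and analysis name the same test, it delivers its planned power, and under stratified randomization it errs only on the safe side. That stands, and it makes this an efficiency point.

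The prognostic evidence is also weaker than it first looks. The statement in Section 2.1 that yield depends strongly on lesion size concerns fluoroscopy-guided transbronchial biopsy, not navigation. Section 2.4 says only that yield appears to be influenced. The one set of yields by size (Section 13, a 33-patient CBCT series) runs the other way: 75% at 20 mm or less and 67% above, an odds ratio of (0.67/0.33)/(0.75/0.25) = 0.68 for larger nodules. Section 3 also limits nodules to 1–3 cm. These points stand and limit the likely gain. With the size effect reversed under CBCT and control-arm odds ratios of 2 or 3, simulations of 16,000 trials per cell gave 0.0 to 1.6 points at nominal critical values and −0.9 to +1.5 with type I error matched. A further check at OR 3 otherwise still found about 1 point.

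Chance imbalance is not bias, and the 5% level already allows for it. That is correct. The argument for adjustment there is precision and a prespecified answer.

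Finally, the proposed test is not exact: its type I error was 5.2% to 5.5% under unstratified blocks, and the size matching used in the power figures would not be applied in practice. The excess is small beside the chi-square's own 5.1% to 5.3%. Section 13.6 does not settle the matter, because its model is about factor effects.

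**Conclusion.** The concern holds as a matter of efficiency and of an undefined design feature. The primary test uses none of the named factors, and the plan does not say whether they stratify the randomization. At the planned rates, adjustment gains about 0 to 4 power points. The upper end needs odds ratios near 4 for both factors, acting alike in both arms. About 1 point is more realistic if the size effect disappears or reverses with CBCT, and under 1 point is lost if no factor matters. The documents give no odds ratios or factor frequencies for the trial population, so the range rests on the stated assumptions. The planned 80% power is sound, and adjustment is a nearly free improvement.

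**What to change.** 1. In Section 1.1 or 13.3, state whether the three factors stratify the randomization.
2. In Section 13.5, and in the matching sentence of 13.2, make the primary comparison a logistic model with arm and the three binary factors as main effects. Report the standardised (marginal) risk difference with a 95% confidence interval and a two-sided p-value from a robust variance with a t reference. A CMH test is a suitable alternative only if randomization is stratified by the factors.
3. Keep the crude chi-square as a sensitivity analysis and as the prespecified fallback if the model does not converge.

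The cost is wording in these sections and a slightly more complex analysis. No new data are needed and 136 patients can stay. In simulation the adjusted test ran at 5.0% to 5.2% type I error under stratified blocks and 5.2% to 5.5% under unstratified blocks.
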